A text-based reduction intervention for smokeless
tobacco cessation

NCT04315506

01/28/2022

Data Analysis Plan

We will use descriptive statistics to summarize the sample characteristics and study measures collected at baseline and longitudinally. We will perform non-directional statistical tests with the significance level set at 0.05 for all analyses. The primary outcome is self-report smokeless tobacco cessation at month 6 (Aims 1 & 3). Due to the exploratory nature of the mediator analyses, the significance level of 0.05 will not be adjusted for the multiple tests associated with steps for determining mediation (Aims 2 & 3). For the efficacy and mediator analyses we will perform, both intention-to-treat (ITT) and completers analyses. ITT analyses will be the primary analyses and will include all participants randomized to an intervention regardless of treatment or study completion. Completers analyses will include only those participants who complete the month 6 assessment, regardless of level of adherence to the SGR or control intervention. Effect sizes and 95% confidence intervals (CIs) will be reported to address clinical significance for the efficacy and mediator analyses. Analyses will be conducted by our faculty biostatistician [name] (Co-I) to ensure application of rigorous methods and implementation of quality assurance procedures. All data will be stored in REDCap at Duke University and downloaded to SAS Version 9.4 for the statistical analysis.

Handling of Missing Data. Missing smokeless tobacco cessation outcome data will be imputed as “did not quit” for the Aim 1 and 3 primary outcome analyses applying the ITT principle. Aim 2 will apply hierarchical mixed-effects trajectory models to assess change in withdrawal symptoms, craving, self-regulation and restraint. Trajectory methods will allow missing outcome data when estimating participant trajectories. To test the data missing at random (MAR) assumption of trajectory methods, intervention group differences in missing rate at each time point and number of missing values across time will be compared using tests for difference in proportion or cumulative counts. For missing covariate data in the models, imputation methods (e.g., multiple imputation) will be carefully applied as needed. The latter will be particularly important for the ITT analyses.

Sample Characteristics. Baseline sociodemographic and clinical characteristics (including tobacco use) will be described for the total sample and by intervention group (SGR vs control). Intervention group differences in baseline characteristics will be examined using t-tests for continuous measures and chi-square /Fisher's Exact tests for categorical variables. Although the randomization should balance the two intervention groups in terms of sample characteristics, the baseline analysis will be used to identify potential covariates to be included in the efficacy and mediation analyses. For example, significant baseline intervention group differences in percentage of participants from rural and/or medically underserved counties will be examined. Statistically non-significant baseline covariates will be omitted from the final analytic models.

Process Measures. Intervention adherence (response to SGR texts for intervention group) and (how often participants read the cessation booklet for control group) and intervention interaction (number of times participants texted the system) for the intervention group and the control group and the effect of these process measures on cessation outcomes will also be explored using correlational analysis. Intervention acceptability will also be examined and compared between arms.

Consideration of Biological Variables. Biological sex and age will be evaluated for their potential covariate or moderating effects on the outcomes regardless of whether the intervention groups

differ on these baseline characteristics (however we do expect a small number of women in the current study given the higher rates of

smokeless use in men). Specifically, the main effect and interaction of each biological variable with intervention group will be tested. For each biological variable, statistically non-significant main and/or interaction effects will be omitted from the final analytic models. If there is a significant interaction (indicative of a moderating effect of the characteristic), the interaction and its component terms will be retained in the final model and a moderator analysis will be conducted applying the approach recommended by Kraemer et al.⁵¹ for clinical trials. For example, if there is a significant sex-by-group interaction effect, the moderating effects of sex will be further evaluated by testing for intervention effects within subgroups of the characteristic. We realize that our numbers of projected females for this study are small given nationally females use smokeless tobacco a very low rate (0.5%)¹¹ and our pilot mirrored these results. Nonetheless, we will conduct analyses to address the influence of these biological factors on study outcomes if there is adequate heterogeneity of the characteristic to do so.

[figure not shown]
Aim 1 Statistical Analysis. We will use logistic regression without covariates to test for an intervention group difference (SGR vs control) in self-reported cessation at 6 months. Next, a covariate-adjusted analysis will also be conducted to evaluate identified potential baseline covariates and examine the impact of biological variables (e.g., age and sex and their interaction with group) on self-reported cessation at 6 months. Odds ratios (ORs) and their 95% CIs will be used to estimate effect size and address clinical significance. As a supplemental analysis, Generalized Estimating Equation (GEE) models for longitudinal binary outcomes will be used to test for intervention group differences in cessation trajectories across the 6 months, with *a posteriori* contrasts at each assessment point. Finally, we will compare self-reported and biochemically confirmed cessation outcomes obtained from 20% random sample of those who self-reported cessation at end of treatment and month 3 and 6. A z-test will be used to test for a group difference in the percent agreement at each time point.

Aim 2 Statistical Analysis. We will use hierarchical mixed-effects models for repeated measures with *a posteriori* contrasts at each time point to test for intervention group differences in the trajectory of changes in severity of craving, withdrawal, self-regulation, and restraints across time (baseline, end of treatment, 3 and 6 months post-intervention). Specifically, random coefficients regression model (RRM) for longitudinal data will be used to compare the rate and pattern of change of these outcomes across time. Fixed effects will be intervention group, time, and group-by-time, while random effects will be participant and participant-by-time. A covariate-adjusted analysis will also be conducted to evaluate the influence of baseline covariates and biological variables (e.g., age and sex effects and their interactions with group). The model will be fitted for significant non-linear change within one or both intervention groups. Intraclass coefficients across time along with Cohen *d* equivalents and their 95% CIs at each time point will be used to address intervention effect sizes.

Exploratory Aim 3 Statistical Analysis. We will conduct mediator analyses using criteria recommended by Baron and Kenny⁵² as well as analytic guidelines from Kraemer et al.⁵¹ to explore whether changes in withdrawal symptoms, craving, self-regulation, and restraint mediate intervention group effects on tobacco use cessation across the 6-months. Each proposed mediator

will be evaluated separately (See **Figure 5**). First, the initial step of the formal mediation analysis will be to determine whether the intervention group significantly influences the trajectory of change in withdrawal symptoms, craving, self-regulation, and restraint (Path A). The Path A analysis will be completed in Aim 2. Second, logistic regression will be used to examine whether the slope coefficients for the individual trajectories of the proposed mediator are associated with cessation at 6 months (Path B). The final logistic regression model conducted for Aim 1 will be used to test for intervention group differences in cessation at 6 months post-intervention (Path C). Finally, the slope coefficients for the proposed mediator will be added as a covariate to the Path C logistic regression model (Path C'). The Path C' analysis will allow us to examine the effects of the intervention groups on Month 6 cessation after adjusting for the effects of change in the proposed mediator across time. For each proposed mediator of SGR effects, mediation will be established if the SGR group compared to the control group has significantly greater improvements in the mediator as an outcome (Path A), the degree of improvements in the mediator across time is related to cessation at 6 months (Path B), the SGR group has a significantly higher cessation rate at 6 months compared to the control group (Path C), and SGR effects on cessation are partially or fully diminished after adjusting for the mediator effect (Path C'). A Sobel's Test will be used to further determine the degree to which improvement in withdrawal, craving, self-regulation, and restraints mediate intervention effects. ORs and their 95% CIs will provide estimates of effect sizes.

Figure 5: Mediation Analysis Pathways

Statistical Power. The sample size of 500 (N=250 per intervention arm) will provide at least 90% power to address the primary aim (Aim 1), primary outcome (self-reported cessation at 6 months), and primary analysis (ITT analysis). A previous smokeless tobacco SGR study in smokeless tobacco resulted in a 27% cessation rate at 6-months.²⁵ Our pilot resulted in a 22% cessation rate at 6-months. Given the improvements to our

SGR intervention, we conservatively estimate a slightly higher quit rate at 25% at 6-months. The Enough Snuff Control intervention has yielded quit rates between 16-18% at 6-months;^{43,44} however, these studies were clinic-based and deployed out of dental offices with military personnel, representing a different population and mode of delivery than we are proposing. A similar, web-based version of the intervention delivered remotely yielded quit rates of 12%.³⁰ Given the low-touch remote nature of our study and the focus on rural and underserved populations, we expect quit rates in the control group to be closer to 12% at 6-months. Therefore, we estimate a medium effect at 6-months. In summary, the target sample size is based on the assumptions that: (1) logistic regression will be performed with two-tailed significance set at 0.05; and (2) the quit rate at month-6 may be as low as 25% in the SGR group and 12% in the control group at 6-months for the ITT analysis (odds ratio of 2.44, Cohen's *d* equivalent of 0.493, approximate medium effect); Consistent with prior smokeless intervention studies, the target sample size will not be adjusted for attrition rate and dropouts will be coded as continued to use. Based on these assumptions, a sample size of 250 per arm will provide 96% power to test the primary aim. If an attrition rate of 30%

is observed in each arm of the proposed study, the resulting sample size of 175 per arm will provide at least 80% power for the completers analysis for Aim 1.

Addressing scientific rigor and reproducibility. All final study procedures will be documented in detail with accompanying scripts, documents, examples and measures. Our assessments and reports will include descriptive statistics. The study PI will oversee the training of study staff and make sure all procedures meet high standards of fidelity using a checklist of key tasks with periodic observations of performance of tasks. Facebook recruitment quality control will be maintained by [name] with consultation from [name]. Texting quality control standards will be maintained under the supervision of [name]. [name] will oversee quality control of all assessment measures during the study. Further, the study statistician, [name], will document data quality control standards and procedures (e.g., data checking).

Potential Risks and Challenges

Assessing adherence. A limitation of the SGR method is that we are not able to objectively determine if smokeless tobacco users actually chew/dip when they text that they do. We considered asking participants to video tape their smokeless tobacco use, but this is burdensome and may reduce intervention engagement. However, assessing adherence is important, and we will conduct daily check-ins at the end of the day via text to ask participants how many times they chewed/dipped that day and if they chewed/dipped off schedule. We will compare these data point to the texts we received throughout the day to verify adherence. In our pilot study, the majority (65%) of participants reported never or only a few times chewing/dipping off schedule. This limitation is outweighed by the multiple strengths of this study, including the focus on a population that has an obvious disparity and minimal access to effective smokeless tobacco cessation interventions.

Plans for non-adherence. Although we found in our pilot work that participants respond to most texts to chew/dip, we will encourage adherence. When participants do not respond to three texts in a row, we will send out a separate text reminding them to respond. Also, at the end of the week, we will send participants a text message letting them know the percentage of texts to which they responded (e.g., “You texted back 89% of the time when we texted. Good job! Try to get to 100%. Thanks so much!”). Those that respond to 80% of weekly texts will be entered into a weekly lottery for a \$25 gift card. Given both groups have two-way texting and are requested to respond to texts, both groups will be entered into this lottery (during the active SGR period for the intervention group and during the 5 weeks of texting for the control group).

Cell phone issues. With any text-based intervention, loss of phone, phone disconnection, and reception are potential risks. We will assess for cell phone reception and possible service disconnection at baseline. We will continually monitor for cell phone problems by monitoring data received by participants to flag participants who have not reported data for extended periods, as well as by instructing participants to report issues to us.

Summary and Future Dissemination Plans

Our text-based SGR intervention has the potential to reach many at risk smokeless tobacco users. Robust preliminary data support the feasibility of our approach in achieving the study aims, and our

research team has a strong record of collaboration. The proposed five-year study (**see Study Timeline**) was designed to examine the effects of text-based SGR cessation compared to evidenced-based standard of care intervention among rural and medically underserved smokeless tobacco users. If this intervention is efficacious, it will be feasible to conduct an implementation trial. The intervention phase is completely automated and our program has the ability to enroll participants via the automated system for future dissemination trials. The long-term goal of this research is to decrease cancer-related morbidity and mortality by developing evidence-based tobacco cessation treatments that are easily disseminable for rural and medically underserved smokeless tobacco users.

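### Choosing covariates by between-arm baseline tests would, on the likeliest reading, keep nicotine dependence out of the adjusted Aim 1 and mediation models in about 95% of trials, leaving the Aim 3 mediator-cessation link open to confounding

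*SAP*

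**What the plan says.** SAP, Sample Characteristics: arms are compared at baseline with t-tests and chi-square or Fisher's exact tests, and "the baseline analysis will be used to identify potential covariates to be included in the efficacy and mediation analyses". The paragraph's example is a significant between-arm difference in rural or underserved status. It closes: "Statistically non-significant baseline covariates will be omitted from the final analytic models".

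SAP, Consideration of Biological Variables, exempts two variables from that comparison, whether or not the arms are balanced on them: "Biological sex and age will be evaluated for their potential covariate or moderating effects on the outcomes regardless of whether the intervention groups". Their terms can still be dropped: "For each biological variable, statistically non-significant main and/or interaction effects will be omitted from the final analytic models". If an interaction is significant, "the interaction and its component terms will be retained in the final model".

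SAP, Aim 1 Statistical Analysis, fixes an unadjusted test: "We will use logistic regression without covariates to test for an intervention group difference (SGR vs control) in self-reported cessation at 6 months". An adjusted model follows it: "Next, a covariate-adjusted analysis will also be conducted to evaluate identified potential baseline covariates".

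SAP, Exploratory Aim 3 Statistical Analysis: for Path C, "The final logistic regression model conducted for Aim 1 will be used to test for intervention group differences in cessation". Path C' adds the mediator's slope to that model. Path B names no covariates. Mediation is declared when Paths A, B and C are all significant in the right direction and the group effect shrinks in Path C'.

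The protocol's Significance section treats nicotine dependence as predictive of quitting, and its Measures section has dependence (SSTDS, scored 0 to 19) collected at all time points. Neither document commits to adjusting for it. The protocol does say that many baseline measures may be explored as moderators or mediators once the aims have been examined, but that does not put dependence into the Aim 1 or Aim 3 models.

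**The concern.** In a randomised trial a between-arm baseline test picks up only chance imbalance. It says nothing about whether a variable predicts quitting, so a strong predictor is flagged no more often than an irrelevant one.

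For the adjusted Aim 1 model this means a data-driven covariate set that usually omits a predictor the protocol itself names. The cost there is mainly precision.

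For Aim 3 the screen looks for the wrong thing. Randomisation balances dependence between arms, but change in craving, withdrawal, self-regulation or restraint is not randomised. If dependence affects both that change and quitting, Path B and the slope term in Path C' are confounded even when the arms are perfectly balanced. What is at stake is the reading of mechanisms, not the efficacy result.

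**Working it through.** **1. The plan's own power.** Inputs (SAP, Statistical Power): 25% vs 12%, 250 per arm, two-sided 0.05. The pooled rate is 0.185.
- SE0 = √(2 × 0.185 × 0.815 / 250) = 0.0347
- SE1 = √((0.25 × 0.75 + 0.12 × 0.88) / 250) = 0.0342
- Power = Φ((0.13 − 1.96 × 0.0347) / 0.0342) = Φ(1.81) = 96.5%, matching the stated 96%
- Odds ratio = (0.25/0.75) / (0.12/0.88) = 2.44, also as stated

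**2. Chance that dependence passes the screen.** By construction this is 5%. In 10,000 simulated trials (permuted blocks of four, 250 per arm) it was 5.0% for a continuous score and 4.8% for an integer 0 to 19 score (mean 10 and SD 4 assumed). Flagging needs an imbalance of at least 1.965 × √(2/250) = 0.176 SD.

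**3. Adjusted Aim 1 model.** The documents give no prognostic strength, so an odds ratio for cessation of 1.5 to 2.72 per SD of dependence is assumed (direction does not matter here). With 20,000 trials per cell:
- Always adjusting raises power from 96.5–96.9% to 96.9–98.3%, a gain of 0.4 to 1.4 points. If the 25% and 12% rates already contain 30% random dropout coded as not quit, the gain is 0.3 to 1.1 points.
- The SAP rule recovers 0.04 to 0.24 points.
- Median chance imbalance is 0.6745 × √(2/250) = 0.060 SD. It moves the expected unadjusted odds ratio from 2.44 to 2.39–2.50 (OR 1.5 per SD) or 2.32–2.58 (OR 2.72 per SD).
- For comparison, the SE of the log odds ratio is √(1/46.875 + 1/26.4) = 0.243, a 95% interval of about 1.52 to 3.94.

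**4. Slope term in Path C'.** Model: the mediator slope depends on arm (0.3 SD difference assumed) and on dependence with correlation r; cessation depends on arm and dependence only, so the mediator has no true effect. Percentage of trials with a significant slope term under the SAP rule (4,000 trials per cell, Monte Carlo SE at most 0.8 points):

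| OR per SD | r = 0.1 | r = 0.2 | r = 0.3 |
|---|---|---|---|
| 1.5 | 6.1 | 9.9 | 17.2 |
| 2.0 | 7.3 | 19.2 | 35.3 |
| 2.72 | 10.9 | 30.9 | 57.8 |

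At r = 0 the figure is about 5%. With dependence always in the model it is 4.0 to 5.8%. A separate simulation (r = 0.3, OR 0.6) gave 22.3% under the SAP rule, 23.4% with no adjustment at all and 4.5% with dependence always included. The rule therefore behaves almost like never adjusting. The mean mediator log odds ratio in that case was −0.14 under the rule and 0.00 with adjustment.

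**5. All four mediation criteria, still with no true mediator effect.** Path A was approximated by a two-sample test on slopes, and Path B significance was taken from the slope term in Path C'.
- If more dependent users improve less on the mediator and quit less, the criteria are falsely met in 4.4 to 50.9% of trials (r = 0.1 to 0.3).
- With the opposite sign the rate is 0.1% at r = 0.3 (OR 2.0 or 2.72) and 0.9% at r = 0.1, OR 1.5 (1,500 trials per cell).
- At r = 0 it is about 2%.

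The near-zero rates are not reassuring. They show the bias working against the pattern the SAP requires, so it would also work against a real mediator.

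**6. What adjustment leaves behind.** The mediator slope runs through month 6 (SAP, Aim 2 Statistical Analysis), the visit at which cessation is assessed, so quitting may itself change the slope. If quitting shifts it by an assumed 0.2 to 0.3 SD (r = 0.2, OR 1.5), the four criteria are falsely met in 59 to 82% of trials under the SAP rule and still in about 38 to 68% with dependence adjusted.

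**The case against.** **The primary result is safe.** A reader might infer that the screen compromises the Aim 1 test or its type I error. It does not: that test is the unadjusted logistic regression, fixed in advance. This stands in full.

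**The 5% depends on a reading.** The SAP says the baseline comparison identifies potential covariates, not that it is the only route. The Aim 2 paragraph mentions baseline covariates without repeating the screen, and Aim 3 also follows cited guidance that is not reproduced. This stands as a caveat. However, exempting age and sex from the between-arm comparison would be pointless if other variables were not subject to it. If non-significant refers to the outcome model instead, a variable must still be identified first, so 5% becomes an upper limit.

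**The size is assumed.** A reader might take 51% false mediation as the expected result. The documents give neither the correlation nor its sign. More dependent users could start with worse craving, decline more steeply and still quit less, which would hide mediation. With zero correlation there is no problem.

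**Adjustment is not a cure.** With dependence in the model, the simulated four-criteria rate falls to 1.8–2.8%, but only if dependence is the sole non-causal link. Step 6 shows why that should not be promised.

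**Retained interactions.** A reader might also infer that a chance age interaction would make the Path C group coefficient uninterpretable. That would need uncentred age coding, which neither document states, and the SAP already prescribes a moderator analysis in that event.

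**Aim 3 is exploratory.** That lowers the stakes. It explains the lack of multiplicity adjustment, but it does not justify an avoidable bias from a variable already being collected.

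**Conclusion.** The point holds in limited form. The screening rule is a poor way to choose covariates and should be replaced, but no stated figure is wrong and the efficacy conclusion is not threatened. In the adjusted Aim 1 analysis the loss is small, about a point of power.

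The material consequence is confined to Paths B and C', where a spurious slope association ranges from no inflation to more than half of trials. That range rests on the assumed correlation of 0 to 0.3 and odds ratios of 1.5 to 2.72 per SD. The direction of the resulting error, invented or concealed mediation, cannot be settled from the documents. The entry rate of about 5% follows from the 0.05 test itself and needs no such assumption beyond the reading of the SAP discussed above.

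**What to change.** - Delete the baseline-significance rule in Sample Characteristics and the drop-if-non-significant rules there and in Consideration of Biological Variables.
- Before outcome data are examined, name a short covariate set: baseline SSTDS score and age at minimum, with baseline chews or dips per day as an option. Keep it whatever the p-values. The documents do not show whether outcome data had accrued by the SAP date, so the timing should be recorded.
- Use that set, without interactions, in the adjusted Aim 1 model and in Paths B, C and C'. Test age and sex interactions in separate moderator models.
- Keep the unadjusted logistic regression as the primary test, with the fixed adjusted model as a prespecified supporting analysis.

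The cost is SAP wording; no new data are needed. There are three downsides. The adjusted odds ratio is conditional, so an adjusted risk difference should be reported beside it. Missing covariates may need the imputation that Handling of Missing Data already allows. Only confounding by the measured baseline covariates is removed, so the Aim 3 report should state that unmeasured confounding and reverse causation through the month 6 visit remain.

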- **Nicotine Addiction.** We will assess nicotine addiction at all time-points using the Severson Smokeless Tobacco Dependence Scale-Short Form (SSTDS). The SSTDS is a validated questionnaire has eight items with a range of scores from 0-19 with higher scores being most addicted to nicotine.⁴⁷
- **Self-efficacy.** At all time-points we will measure self-efficacy using a similar 9 item scale to the Temptations scale. We will adapt the scale by switching out smoking with chewing/dipping. Sample items read, "How

confident are you that you would not chew in the following situations: when you are very angry about something or someone, when you feel you need a lift, etc." (1=Not at all confident and 5=Extremely confident).

- Alcohol Use Disorder Identification Test (AUDIT-3). At all time-points we will use the AUDIT, a 3 item self-report scale that measures risky drinking, as this may influence quit rates.⁵⁰

Process Measures: Process measures that could impact outcomes will be collected at baseline, during intervention administration, at the end of treatment, 3 and 6 month follow-up.

- Adherence (Intervention Group). Adherence to the SGR intervention will be calculated two ways. First, we will measure time to response from the SGR message. Second, we will create a categorical variable (0=respond in more than 30 minutes, 1=respond after 30 minutes. If a participant responds to less than half of chewing/dipping prompts in one day, we will exclude this day from the adherence analysis examining whether overall adherence predicts quit rate and/or smokeless reduction in the SGR group.
- Adherence (Control Group). Participants will be asked at all follow-up time points how often they read the cessation booklet using a using a 5-point Likert scale (1 = none, 2 = some, 3 = most, 4 = the entire guide, and 5 = the entire guide more than once).⁴⁴
- Satisfaction with Intervention. Participants in both arms will be asked at end of treatment survey 1) "How useful was the intervention in helping you to quit smokeless tobacco?" (Not at all useful=1, Extremely useful =5) and 2) "Would you recommend the program to a friend?" (Definitely would not recommend=1, Definitely would recommend=5).

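### The adherence and text-count analysis is an unadjusted correlation worded as an effect, with no stated coding for missing cessation outcomes (minor)

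*SAP*

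**What the plan says.** The SAP (Process Measures) lists response to SGR texts, booklet reading in controls and, in both arms, the number of texts a participant sent. It then states that "the effect of these process measures on cessation outcomes will also be explored using correlational analysis". No covariate, outcome coding or completers version is named. Every test in the plan is two-sided at 0.05.

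The nearby rules do not clearly reach this analysis:

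- **Missing outcomes.** Handling of Missing Data sets missing cessation to not quit "for the Aim 1 and 3 primary outcome analyses applying the ITT principle". Statistical Power says more generally that "dropouts will be coded as continued to use".
- **Completers.** "For the efficacy and mediator analyses we will perform, both intention-to-treat (ITT) and completers analyses"; process measures are not mentioned.
- **Covariates.** Baseline covariates are selected for the efficacy and mediation models only.

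The protocol (Process Measures) adds a scoring rule for SGR adherence that the SAP does not repeat: "If a participant responds to less than half of chewing/dipping prompts in one day, we will exclude this day from the adherence analysis". For controls, "Participants will be asked at all follow-up time points how often they read the cessation booklet".

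**The concern.** There are two separate problems.

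**Confounding by baseline use.** The SGR schedule is built from each participant's own average chews per day, so heavier users receive more alerts and have more occasions to text. The protocol (Significance) says dependence predicts cessation. Baseline use therefore sits behind both variables. For text counts the sign is not predictable. Engagement pushes it up. Heavy use, off-schedule chews and slips, all of which generate texts, push it down.

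**Unstated outcome coding.** If missing = not quit is carried into this correlation, and participants with low response are more often missing at month 6, low adherence and imputed failure arrive together. That builds in a positive correlation.

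At stake is what the trial says about adherence, which the protocol wants to examine as a predictor of quitting and which would inform later implementation work. No primary or secondary aim depends on it.

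**Working it through.** **Inputs from the documents.** 250 per arm; 25% (SGR) and 12% (control) quitting under ITT; a 30% attrition scenario; two-sided 0.05. The plan gives no figure for the adherence analysis. Its 96% power for the primary comparison reproduces (96.5%), and 250 × 0.70 = 175 matches its completers number.

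**1. How far texting follows baseline use.** In the protocol's sample schedule (8 chews a day), week 1 has 8 × 7 = 56 self-monitoring texts and weeks 2–6 have (6+4+3+2+1) × 7 = 112 alerts, 168 in all. On a proportional schedule, someone with half the use has about half as many. Control prompts are fixed at 2 × 5 = 10, so this route applies to the SGR arm.

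**2. Size of the confounding.** Let the text count have no effect, let quitting have odds ratio OR per SD of baseline use, and let count and baseline use correlate at ρ. Then r ≈ ρ × ln(OR) × √(p(1−p)), and the probability of significance is about Φ(|r|√n − 1.96). Take p = 0.25, n = 250 and ρ = 0.8 (OR and ρ are assumptions).

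- OR 0.8: r ≈ 0.8 × (−0.223) × 0.433 = −0.077; |r|√n = 1.22; Φ(−0.74) = 23%.
- OR 0.6: r ≈ 0.8 × (−0.511) × 0.433 = −0.177; |r|√n = 2.80; Φ(0.84) = 80%.

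Simulation gave 22% to 79% over the same range of odds ratios, and about 6% after adjusting for baseline chews.

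**3. Coding route, closed form.** With no adherence effect and 30% missing, the quit rate among those observed is 0.25/0.70 = 35.7%. Split the SGR arm at the median of adherence (125 each) and code missing as not quit. For 20% missing in high adherers and 40% in low adherers, the coded rates are 0.357 × 0.80 = 28.6% and 0.357 × 0.60 = 21.4%. The odds ratio is (0.286/0.714)/(0.214/0.786) = 1.47. The SE is √(2 × 0.25 × 0.75/125) = 0.0548, so z = 0.0714/0.0548 = 1.30 and Φ(1.30 − 1.96) = 26%.

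| Missing, high / low adherers | Spurious OR | False positives |
|---|---|---|
| 30% / 30% | 1.00 | 5% |
| 25% / 35% | 1.21 | about 10% |
| 20% / 40% | 1.47 | about 26% |
| 15% / 45% | 1.78 | about 50% |
| 10% / 50% | 2.18 | about 74% |

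With a continuous score, and log-odds of being missing falling by 0.25, 0.5, 1.0 or 2.0 per SD of adherence, simulated false positives are 10%, 25%, 64% and 95%. Using observed outcomes only gives 4–6%, provided missingness depends on adherence alone.

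**4. The day-exclusion rule.** Assume 40% of the SGR arm stop texting, and 50% of stoppers against 17% of others miss month 6. Response over all prompts is falsely significant in 33% of trials. With the protocol's rule applied it is 4%, because silent days leave the score. That protection needs response before stopping to be unrelated to stopping. If eventual stoppers already replied 10, 20 or 30 points less, the rate is 12%, 26% or 35%. The rule does not touch the text count.

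**5. Is observed-only the right replacement?** Let missingness also depend on quitting (n = 250, 30% missing, true quit rate 25%, no adherence effect, log-odds of missing falling by 1 per SD of adherence).

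| Quitters' log-odds of missing lower by | Observed only | Missing = not quit |
|---|---|---|
| 0 | 6% | 46% |
| 1 | 15% | 23% |
| 2 | 31% | 11% |
| 4 | 52% | 5% |

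Neither version is better throughout.

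**The case against.** The strongest reply is that the SAP is silent here rather than wrong. The not-quit coding is written for Aims 1 and 3, the broader dropout sentence sits among the sample-size assumptions, and the analysis is called exploratory. This stands: the coding artefact is conditional on a choice the SAP does not state.

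A reader might infer that participants who stop texting are automatically scored as failures. The documents do not support that. Only a missing assessment triggers the code, and the protocol (Recruitment and Data Collection) seeks follow-up from everyone whatever their adherence, by phone or smartphone survey, with backup contacts and graded payment. The pilot still retained only 70%, so a link between disengagement and missingness is plausible, but its size is unknown.

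A reader might also infer that the trial will report SGR adherence, but not booklet reading, as driving quitting. No between-arm comparison of these correlations is planned, and controls also have a log-based text count. What remains true is that a control with no follow-up has no booklet-reading value, while an SGR dropout can still have an adherence score.

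Preferring regression to correlation could be called taste. The adjustment is not: the plan's own schedule and its own statement about dependence create the confounding.

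**Conclusion.** The point holds as a minor one. The planned correlation is confounded by baseline use and dependence, most directly for text counts in the SGR arm, where the bias can run either way. Under the assumed odds ratios of 0.8 to 0.6 per SD, false positives are 22% to 79%; the documents give neither those odds ratios nor the correlation between text count and baseline use.

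The outcome coding is an omission with a conditional consequence. False positives run from 5% with no adherence–missingness link to 95% with the strongest link examined, and the documents do not locate the trial in that range. The day-exclusion rule, if carried into the analysis, largely closes this route for the response measure when response before stopping is unrelated to stopping.

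It would go too far to conclude that observed outcomes should simply replace the coded version, since that fails when non-quitters are more often missing. The primary result is untouched.

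**What to change.** In the SAP's Process Measures paragraph:

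1. Replace the correlation with logistic regression of month-6 cessation on each process measure, within each arm, adjusted for baseline SSTDS and baseline chews or dips per day.
2. Show each result twice, side by side: observed month-6 outcomes only, and missing coded as not quit. Say that neither is unbiased under every missingness pattern.
3. State whether the protocol's day-exclusion rule applies to the response measure, and that it does not apply to the text count.
4. Note that controls without any follow-up have no booklet-reading value, and report how many there are.
5. Call the result an association, not an effect.

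The cost is a few sentences and a few lines of code; both covariates are already collected at baseline. At 30% attrition the observed-outcome version uses 175 rather than 250 per arm. The expected number of quitters is 0.25 × 250 ≈ 62 in SGR and 0.12 × 250 = 30 in control, or about 21 and 10 per term in a three-term model. That is workable, though the control estimates will be imprecise.
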